### **12.2 Derived and Transformed Data**

Baseline will be considered to be the latest value obtained before study drug administration (e.g. Visit 2; or Visit 1 if not recorded elsewhere).

Laboratory data will be reported in standard units. Out-of-range laboratory tests may be repeated. If a test is out-of-range at a baseline timepoint and repeated before dosing, the latest repeat value before dosing will be used as baseline. However, if a test is out-of-range and repeated at any other time during the study, the out-of-range value (not the repeat value) will be included in statistical summaries.

### **12.3 Assessment Windows**

There is a +/- 4 day window for clinic visits. Visit 2 can take place on the same day as visit 1, or up to 2 weeks later.

For the safety and ITT populations, all data will be analysed as recorded (regardless of the assessment windows).

## **12.4 Values of Potential Clinical Importance**

Laboratory results identified as ‘clinically significant’ in the CRF will be considered to be potentially clinically important.

QT, QTcB or QTcF > 450 msec and increases in QT, QTcB or QTcF from baseline (Visit 2) of > 30 msec will be considered to be potentially clinically important.

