4.3 Risk-benefit analysis

What are the potential risks of harm to the trials patients from YF476 and from the trial procedures, and how might they be mitigated?

Reported adverse events and potential risks

In all studies in healthy volunteers, YF476 was well tolerated. Adverse events were minor, transient, occurred in subjects given placebo or comparators as well as YF476, and were not YF476-dose dependent. YF476 did not affect: vital signs; ECG; or safety tests of blood and urine. There was no evidence of effect on QT interval in human studies, but *in vitro* studies showed that YF476 has a low potential for prolonging QT interval (See Section 3.2.1). So, until we have more information about YF476, patients with prolonged QT interval are excluded from clinical trials.

The adverse effects that occurred at a frequency of 10% or greater were: abdominal distention, diarrhea, abdominal pain, nausea, and headache. None of these adverse effects were observed with greater frequency as compared to placebo or comparators.

Because of the pancreatic findings in the 13-week toxicology study of dogs (Section 3.2.1), serum amylase and lipase will be monitored at each visit. Also, any patient who complains of abdominal discomfort at any time during the study will be seen immediately by the investigator or delegate and evaluated with history, physical examination, and laboratory tests, including serum amylase and lipase, and other appropriate tests, including radiological investigations.

Risk from concomitant medications

In vitro studies have shown that the likelihood of a drug-drug interaction in patients *in vivo* is:

- CYP2C8: possible for 50–400 mg YF476
- CYP3A4 (testosterone): remote for 50 & 100 mg YF476, and possible for 200 & 400 mg
- CYP3A4 (midazolam): remote for 50 mg YF476, and possible for 100–400 mg.

Although YF476 caused some irreversible inhibition of CYP3A4, the degree of inhibition makes a drug-drug interaction in patients *in vivo* unlikely. And, a clinical study (T-007) of YF476 and midazolam (a substrate of CYP3A4) alone and in combination showed that neither medicine affects the pharmacokinetics of the other (see YF476 Investigator's brochure for further details).

Many medicines are metabolised via CYP3A4/5. Very few are metabolised via CYP2C8. Examples of the main types of medicine that are metabolised by CYP3A4/5

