5.2 Exclusion criteria

1. Histologically confirmed BE with high-grade dysplasia.
2. Histologically confirmed diagnosis of invasive carcinoma of the esophagus.
3. Histologically confirmed BE with low-grade dysplasia that has been diagnosed by at least two expert gastrointestinal pathologists.
4. Prior endoscopic therapy for Barrett's esophagus, including (but not limited to) mucosal resection, radiofrequency ablation, and photodynamic therapy.
5. A relevant history of esophageal or gastric surgery that, in the investigator's opinion, could compromise the objectives of the trial.
6. History of atrophic gastritis, pernicious anemia, or Zollinger-Ellison syndrome.
7. Participation in a trial of an IMP within the previous 28 days.

8. Prolonged QTc interval (>450 msec)
9. History of allergic reactions attributed to compounds of similar chemical composition to YF476.
10. History or baseline findings of:
 - diabetes mellitus requiring insulin therapy;
 - pancreatitis (baseline amylase and/or lipase $\geq 2.0 \times$ ULN);
 - hepatitis B or hepatitis C;
 - HIV, unless, at the discretion of the PI, with at least 120 days on stable ART with undetectable HIV viral load and CD4 >350 cells/mm³;
 - malabsorption syndrome or inability to swallow or retain oral medicine;
 - major surgery ≤ 28 days prior to enrollment;
 - ECOG performance status ≥ 2 ; or
 - cancer within 3 years except for basal carcinoma of the skin or cervical carcinoma in-situ.
 - Also, any clinically significant and uncontrolled major morbidity including but not limited to: serious cardiac disease (unstable angina, s/p myocardial infarction ≤ 1 month); respiratory disease (advanced COPD or pulmonary fibrosis); uncontrolled hypertension; active systemic infection; or psychiatric illness/social situations that would limit compliance with study requirements.
11. Certain medicines and herbal remedies (see Appendix B) taken during the 7 days before the start of study drug.
12. A history of cancer >3 years from the time of enrollment, and the patient is not up to date with surveillance for that cancer (based on national guidelines), or has evidence of cancer at the time of enrollment.

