10.3 Laboratory methods

10.3.1 Laboratories

All tissue biomarker analyses will be performed in the laboratory of [name] (Columbia University, New York, NY). Histological review of specimens, including IHC assessment of Ki67, p53, and DCAMKL1 expression, will be performed by [name] (Columbia University, New York, NY). Routine testing of blood and urine specimens will be performed locally.

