### **14.5 Clinical Laboratory Evaluations**

Data from haematology, clinical chemistry and urinalysis will be summarised by treatment group.

All laboratory values of potential clinical importance will be listed and all related laboratory results (i.e. haematology or clinical chemistry) for patients with values of potential clinical importance will be listed, separately. Frequencies of laboratory values of potential clinical importance will be summarised.

Urinalysis parameters will also be listed.

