**Template T\_LB2**

Table 14.3.5.xx Summary of Chemistry Laboratory Values

Laboratory Test (units)	Treatment	Visit	n	Mean	SD	Median	Min	Max	n	Change from Baseline				
										Mean	SD	Median	Min	Max
	Treatment 1 (N=xx)													

Source: Listing 16.2.xx

*Programming notes:* Continued with all treatments and time points For Ki67 Expression data exclude first column

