**Template L\_LB1\_PG**

Listing 16.2.x.xx Listing of clinical chemistry abnormalities of potential clinical importance

Treatment	Subject	Laboratory test (units)	Planned Relative Time	Date/Time	Study Day	Value	Reference Interval	Clinically Significant?
Treatment 1	1001	Alk Phos (U/L)	Time 1	01JAN2002 13:34	-1	64.00	32.0 - 92.0	Y
			Time 2	01APR2002 07:22	85	84.00	32.0 - 92.0	Y
		ALT (U/L)	Time 1	01JAN2002 18:56	-1	29.00	10.0 - 40.0	Y
			Time 2	01APR2002 09:22	85	70.00	10.0- 40.0	Y

*Programming notes:* Lists only Laboratory results identified as 'clinically significant' in the CRF

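### SAP 12.4 has no numeric reporting rule for amylase or lipase, so rises the investigator does not mark clinically significant are not counted by arm in Table 14.3.4

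*SAP*

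**What the plan says.** **Why the pancreas is watched.** Protocol 3.2.1 reports altered pancreas weight and histology in some dogs in the 13-week study and a raised amylase in one. A drug effect could not be ruled out and no NOAEL was clearly set. Protocol 4.3 therefore provides that "serum amylase and lipase will be monitored at each visit". It also asks for these tests, at any time, in a patient who complains of abdominal discomfort. The same section names a second risk, QT prolongation.

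**How a laboratory value becomes important.** Results marked clinically significant "in the CRF will be considered to be potentially clinically important" (SAP 12.4). The shell for the supporting listing repeats the filter: "Lists only Laboratory results identified as 'clinically significant' in the CRF". SAP 14.5 adds that "Frequencies of laboratory values of potential clinical importance will be summarised"; this is Table 14.3.4. For QT, QTcB and QTcF, by contrast, SAP 12.4 uses values above 450 msec and increases above 30 msec.

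**What does not depend on the mark.** SAP 14.5 also says "Data from haematology, clinical chemistry and urinalysis will be summarised by treatment group". The shell "Summary of Chemistry Laboratory Values" (T_LB2, used for Table 14.3.5.1) gives n, mean, SD, median, minimum and maximum by treatment and visit, with the same statistics for change from baseline. Complete listings of all data are planned too.

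**The one numeric level in the documents.** Protocol 5.2 excludes patients with "pancreatitis (baseline amylase and/or lipase" at or above 2.0 x ULN). It applies at entry. Neither document sets a level for reporting on-treatment values.

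**Where samples are tested.** "Routine testing of blood and urine specimens will be performed locally" (protocol 10.3.1), at two sites.

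**The concern.** The scheduled amylase and lipase tests are there to detect a pancreatic effect. The only planned output that counts laboratory abnormalities by arm depends wholly on a judgement made patient by patient at two sites. Read alone, a zero in Table 14.3.4 could mean that nobody had a rise, or that rises occurred and were thought unimportant. An asymptomatic enzyme rise is the kind of result an investigator may leave unmarked.

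With about 10 patients per arm, one or two cases may be the whole signal. The QT risk, named in the same protocol section, is counted by a rule that any analyst would apply identically; the pancreatic risk is not.

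**Working it through.** The plan states no figure on this point, so there is none to reproduce. The check traces one result through the outputs and then illustrates the size.

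**Step 1. Follow an unmarked on-treatment rise.**

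| Output | Does it appear? |
|---|---|
| Table 14.3.4 (count by arm) | No: filtered on the mark |
| Listings 16.2.8.1 and 16.2.8.3 | No: same filter |
| Listing 16.2.8.2 (all chemistry for flagged patients) | Only if another chemistry value of that patient is marked |
| Table 14.3.5.1 (raw-unit summary by arm and visit) | Yes, if taken at a scheduled visit; SAP 12.2 keeps the out-of-range value rather than the repeat |
| Complete listings, sorted by treatment (SAP 11.1 and 19.1) | Yes |
| Adverse event tables | Only if the investigator reports it (protocol 11 allows an abnormal laboratory finding as an event) |

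A for-cause test between visits fares differently. SAP 12.1 keeps results from unscheduled time points out of summaries and shows them only in listings. An amylase or lipase drawn because of abdominal discomfort is therefore absent from Table 14.3.5.1 as well.

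**Step 2. What Table 14.3.5.1 can show.** Assume an arm of 10, each patient at 0.5 x ULN, one rising to 2.1 x ULN and nine flat.

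- Maximum: 2.1 x ULN.
- Median: 0.5 x ULN, unchanged.
- Mean: moves by (2.1 - 0.5)/10 = 0.16 x ULN.

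For baselines of 0.3 to 0.8 and peaks of 2.1 to 3.0 x ULN, the mean moves by between (2.1 - 0.8)/10 = 0.13 and (3.0 - 0.3)/10 = 0.27 x ULN.

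The maximum shows that an extreme value occurred, but it stays at 2.1 whether one, two, three or four patients reach that level, and the median stays at 0.5 in all four cases. The table also reports raw units pooled over two laboratories. A raw value x equals x/ULN at the laboratory that measured it; if the two ULNs differ, the pooled maximum cannot be read as a multiple of either. The documents give no site ranges, so whether they differ is unknown.

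**Step 3. Size of the effect on Table 14.3.4.** Let r be the true proportion of patients with a value past the chosen level and f the proportion of those marked. With n = 10 per arm (SAP 8.1), the chance of at least one counted case is 1 - (1 - r f)^10. For r = 10%:

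- f = 1: 1 - 0.9^10 = 0.651
- f = 0.5: 1 - 0.95^10 = 0.401
- f = 0.25: 1 - 0.975^10 = 0.224

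| Assumed r | All marked (same as a numeric rule) | Half marked | A quarter marked |
|---|---|---|---|
| 5% | 40% | 22% | 12% |
| 10% | 65% | 40% | 22% |
| 20% | 89% | 65% | 40% |
| 30% | 97% | 80% | 54% |

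With no marks the chance is 0% at every rate. Neither r nor f comes from the documents.

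**The case against.** The strongest reply is that the data are displayed anyway. Table 14.3.5.1 carries the maximum and the maximum change by arm, and the complete listings are sorted by treatment. With 20 planned completers, a reader can go through every amylase and lipase result. This stands: a reader might infer that an unmarked rise disappears from all by-arm output, and the documents do not support that. It is missing from the count and from the listings built on the mark.

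Second, 2.0 x ULN is an entry criterion. A reader might infer that the SAP disregards a protocol safety limit. It does not, because the protocol sets no on-treatment limit for these enzymes. Using 2.0 x ULN as a reporting category is a convenience, and another multiple could be chosen.

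Third, no commitment is broken. Protocol 13.6.2 asks only for summaries of values and of change from baseline, and the SAP delivers both. The QT cut-offs were already in protocol 13.6.3, so the contrast between QT and pancreas starts in the protocol. Nor is the pancreas the only named risk; it is the named risk without a numeric reporting rule.

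Fourth, investigators and patients are blinded and randomization is stratified by site, so there is no stated reason why under-marking should favour one arm. This also stands: the cost is sensitivity and reproducibility of one table, not demonstrated bias.

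What the reply does not supply is a by-arm count of patients that two analysts would reproduce, or any place in the summaries for the for-cause tests that protocol 4.3 calls for.

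**Conclusion.** The point holds as a gap in reporting. The by-arm laboratory count and its listings rest entirely on the investigator's mark, and amylase and lipase have no numeric rule although they are tested at every visit for a stated reason. The other displays show individual values or an extreme, not the number of patients past a level, and the summaries omit unscheduled tests.

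The 65%, 40% and 22% are illustrative. They rest on an assumed event rate, assumed marking rates and 10 patients in the arm. They give the chance that Table 14.3.4 is not empty, not the chance that the trial displays the value; for a scheduled value, Table 14.3.5.1 and the complete listings do not suffer that fall. The primary endpoint and access to the data are unaffected. The change is worth making because it is cheap and replaces a subjective count with a reproducible one.

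**What to change.** In SAP 12.4 and Table 14.3.4, keep the investigator's mark and add beside it the number of patients per arm with amylase or lipase at or above a fixed multiple of the local laboratory's ULN:

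- by visit, and at any post-dose time, with the any-time count stated to include unscheduled results as an exception to SAP 12.1;
- as a count of patients, stated explicitly, since the note on shell T_LB1 defines n as results;
- with a listing of those patients whether or not the value was marked.

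The 2.0 x ULN already used at entry can serve as the category, for reporting only and not as a treatment rule.

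Cost: a few lines of SAP text and programming. The values are collected, shell L_LB1_PG already has a reference-interval column, and protocol 14.1.2 requires laboratory normal ranges. The small downside is that some benign transient rises will be counted; showing the investigator's mark alongside lets the reader weigh them.

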## **13 Study Population**

### **13.1 Disposition of Patients**

The disposition of all patients in the safety population will be summarised (by site and overall) including number of patients randomised, number completing the study by treatment, and number withdrawn from the study. The number of screen failures will also be summarised and listed.

All patients who withdraw or are withdrawn from the study will be listed by treatment, with the reason for withdrawal.

A listing of analysis populations will be provided.

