5.4 Recruitment and retention plan

There will be 2 study sites: Columbia University Medical Center (CUMC), New York, US, and the National Institute for Health Research (NIHR) Clinical Investigation Ward (CIW), Cambridge University Hospitals, Cambridge, UK. Eligible patients will be recruited from the clinical practices of the study investigators ([name]). All of the study investigators see a large volume of patients referred for management and treatment of Barrett's esophagus. We aim for 20 patients to complete the trial. Recruitment progress will be assessed on an ongoing basis. Screening and enrollment logs will be regularly reviewed by the investigators. Patient withdrawals will be

carefully monitored. Methods for patient retention will be implemented, including the maintenance of regular contact with study patients. The study staff will meet regularly to review issues related to recruitment and retention, identify areas of improvement, and implement appropriate strategies to address any deficiencies. Additional recruitment methods such as advertising may be performed by each individual site with the approval of that site's Institutional Review Board or REC.

Withdrawals will be replaced at the discretion of the investigator.

6 Administration of study medication

Study medication will be dispensed on an outpatient basis, and self-administered by patients. Reported adverse events and potential risks are described in Section 4.3.

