6.7 Compliance

- All randomized patients will be eligible for statistical analysis. Patients will be analyzed on an intent-to-treat basis, and also per protocol.

-
- Compliance will be measured by capsule counts at the Week 6 and Week 12 visits, and by review of patient diary cards.

[figure not shown]
7 Pharmaceutical information

YF476 (IND # 107354, IND Sponsor: Trio Medicines Ltd)

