13.2 General Statistical Considerations

The null hypothesis is that there is no difference between YF476 and placebo in the treatment of patients with Barrett's esophagus, the alternative hypothesis is that there is a difference between the treatments. Statistical significance will be defined as $p \leq 0.05$.

Statistical analysis will be done by HMR. The statistical package SAS (version 9.2) will be used to produce all summary tables and data listings.

For the data analysis, missing or dropout data will not be imputed; analyses will be performed only on observed data. In this study, there will be no significance level adjustment for multiplicity.

Quantitative data will be tabulated with descriptive summary statistics: arithmetic mean, standard deviation, median, minimum and maximum values, and number of observations. Geometric mean and geometric CV% will be provided for C_{\max} and C_{trough} . For categorical data, frequency tables will be provided.

A detailed Statistical Analysis Plan (SAP) describing the methodology to be used in the final analysis will be prepared by the HMR Statistics and Data Management Department after completion of the final protocol. Any deviations from the planned statistical analyses in the protocol will be fully described in the SAP.

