13.7 Determination of sample size

Based on our preliminary data, we estimate a mean baseline Ki67 index of 45–50%, with a common SD of 14–18%. Assuming a two-sided type I error rate of 0.05, a sample size of 20 (10 per arm) has 98% power to detect a 30% absolute difference in $\Delta Ki67$ between the two arms if the common SD is 16%, and 97% power for a 25% difference with a 14% common SD (see Table 1).

Table 1. Power calculations based on 20 patients (10 per arm)			
	$\Delta\text{Ki67}_{\text{YF}} - \Delta\text{Ki67}_{\text{pl}}$		
SD	0.25	0.30	0.35
0.14	97%	99%	>99%
0.16	91%	98%	>99%
0.18	84%	94%	98%

14 Ethical and regulatory considerations

This trial will be conducted in compliance with the protocol, Good Clinical Practice (GCP), and the applicable regulatory requirements.

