## 9 Analysis Populations

The following populations will be identified:

Screened Population: All patients screened for the study.

Safety Population: All patients who are randomised and received at least one dose of the study drug. In this population, treatment will be assigned based upon the treatment patients actually receive regardless of the treatment to which they were randomized.

Intent-to-Treat (ITT) Population: All randomised patients who receive at least one dose of study medication and had at least one post-baseline assessment. In this population, treatment will be assigned based upon the treatment to which subjects were randomised regardless of which treatment they actually received.

Per Protocol (PP) Population: All randomized patients who receive at least one dose of study medication and had at least one post-baseline assessment and did not have any major protocol deviations.

In all populations (apart from ITT) treatment will be assigned based upon the treatment patients actually receive regardless of the treatment to which they were randomised.

The primary endpoint will be analysed using the ITT population.

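### The SAP counts randomised patients inside a dosed population, and the primary Ki67 result is a paired-biopsy result on a modified ITT set with no missing-data check

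*SAP*

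**What the plan says.** **Disposition.** SAP 13.1: "The disposition of all patients in the safety population will be summarised (by site and overall) including number of patients randomised". SAP 9 admits to the safety population only randomised patients who took at least one dose. SAP 19.1 assigns Table 10.1 to that population. Its shell (T_SD1, SAP 19.2.1) has blocks for Screened, Safety, Intent to Treat and Per Protocol, and none for Randomised.

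**Analysis set.** SAP 9 defines ITT as "All randomised patients who receive at least one dose of study medication and had at least one post-baseline assessment" and assigns the primary endpoint to it. Protocol 13.1 defines ITT in the same terms. Protocol 6.7 says: "All randomized patients will be eligible for statistical analysis". SAP 12.1 says that everyone who withdraws early from the study or the drug is included in the analyses.

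**Missing data.** Protocol 13.2: "missing or dropout data will not be imputed; analyses will be performed only on observed data". Ki67 comes from biopsies at baseline and Week 12 only (Protocol 4.1). The single sensitivity analysis in Protocol 13.4 is an analysis of covariance on baseline.

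**Replacement.** Protocol 5.4: "Withdrawals will be replaced at the discretion of the investigator". Protocol 8.8 keeps enrolment open until at least 20 patients have finished treatment, the second endoscopy and follow-up.

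**The concern.** A count of randomised patients cannot be taken correctly inside a set that excludes the undosed. In a trial of about 10 per arm, one missing patient is a visible part of an arm, and the reader needs the randomised number by arm to judge balance.

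The label matters as well. A reader told that the primary result is ITT will assume that all, or nearly all, randomised patients are represented. In fact a patient without a Week 12 biopsy adds nothing to the Ki67 comparison. Because withdrawals can be replaced, the number analysed can reach 20 whatever the losses were. If losses differ by arm and are related to response, the paired-biopsy difference would not be the difference for all randomised patients, and nothing planned would show by how much.

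**Working it through.** **1. Can a randomised patient be undosed?** Patient numbers are allocated immediately before the Visit 2 endoscopy (Protocol 7.6). The first dose is taken the day after (Protocol 8.2). The window is about a day, so this is possible, though no document says that it has happened.

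**2. Where would that patient appear?**
- Safety, ITT and Per Protocol blocks: no, because each requires a dose.
- Screened row: yes, but it mixes randomised patients with screen failures. SAP 9 also assigns treatment in every set except ITT by what was actually received, so an undosed patient has no defined treatment column there.
- Listings: yes. Withdrawals are listed with reasons (SAP 13.1), population membership is listed (L_AN1_PG), and complete listings are planned (SAP 19.1).

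The randomised count by arm and site is therefore short by exactly the number randomised and not dosed.

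**3. Losses on baseline histology.** Protocol 8.7.2 withdraws patients whose Visit 2 biopsies do not qualify, which is after allocation. The time to a pathology result is not stated. Such a patient could be undosed (outside Safety), dosed without a later assessment (in Safety, outside ITT), or dosed with one (in ITT, without a Week 12 Ki67). T_SD1 has no reason line for this, so these patients would fall under a general one such as protocol violation or other.

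**4. Who contributes to the primary comparison?** Any post-baseline assessment, for example Week 6 vital signs, qualifies a patient for ITT. Only a baseline and a Week 12 index give a ΔKi67. With no imputation, the analysed patients are those with paired biopsies.

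**5. Does the stated power depend on this?** Inputs from Protocol 13.7: a two-sided test at the 5% level; "a sample size of 20 (10 per arm) has 98% power to detect a 30% absolute difference" at SD 16%; and an SD range given as "with a common SD of 14–18" per cent.
- Noncentrality = 0.30 / (0.16 × √(2/10)) = 4.19; df = 18; critical t = 2.101.
- Power = 97.7%, against 98% stated.
- The other eight cells of Table 1 also reproduce within 2 points by the same noncentral-t method.

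The 20 are completers (Protocol 4.1), so the power statement stands.

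**6. How many could fall outside?** No dropout rate is stated. Number to randomise for 20 evaluable = 20/(1 − loss), rounded up:

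| Assumed loss | 5% | 10% | 15% | 20% | 25% | 30% |
|---|---|---|---|---|---|---|
| Randomised | 22 | 23 | 24 | 25 | 27 | 29 |
| Outside the Ki67 analysis | 2 | 3 | 4 | 5 | 7 | 9 |

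**7. Illustrative effect on the estimate.** Assume 10 active patients with paired biopsies, an observed difference of 30 points, k further active patients without a Week 12 biopsy who would have changed like placebo, and no loss on placebo. Then the difference over all = 30 × 10/(10 + k):
- k = 1: 300/11 = 27.3
- k = 2: 300/12 = 25.0
- k = 3: 300/13 = 23.1

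If the k patients are among 10 and not replaced, 30 × (10 − k)/10 gives 27, 24 and 21. If the lost patients would have changed like the others in their arm, the shift is zero.

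**The case against.** A reader might infer four stronger things that the documents do not support.

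- *Undosed patients disappear from every output.* They do not. They belong to the Screened population and to the listings. What is missing is a summary row.
- *Attrition by arm cannot be judged at all.* T_SD1 gives completed and withdrawn counts, with reasons, by arm and site for the Safety and ITT blocks. The gaps are the randomised base and the paired-biopsy count.
- *The ITT definition makes Ki67 a completers-only result.* The definition is broad. The loss comes from one post-baseline Ki67 reading without imputation, and an all-randomised set would lack the same values. Nor is it strictly completers: Protocol 8.7.1 continues endpoint collection, where possible, after study medication stops, so off-drug patients can contribute a biopsy.
- *The SAP departed from the protocol's ITT set.* Protocol 13.1 has the same definition. The tension is within the protocol (6.7 against 13.1) and within the SAP (12.1 against 9).

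Two further objections also stand in part. SAP 3 leaves efficacy data other than gastrin and CgA to separate reporting, so a Ki67 missing-data plan may exist elsewhere. But SAP 9 still fixes the primary set, and Protocol 13.4, which describes the Ki67 analysis, has no such plan. Second, imputing over literally all randomised patients would be wrong: Protocol 10.3.2 defines the index on biopsies with intestinal metaplasia, so a patient withdrawn for lack of it has no baseline to change from.

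**Conclusion.** The point holds as a reporting and labelling defect with a missing sensitivity analysis. The randomised count planned in SAP 13.1 is wrong whenever anyone is randomised and not dosed; its size is the number of such patients, which may be zero. The set called ITT is a modified ITT, and the primary Ki67 result is observed-case. The baseline-adjusted analysis does not test that.

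The figures of 27.3, 25.0 and 23.1 rest on assumed losses confined to the active arm with placebo-like change. They show possible scale and do not predict bias. The power calculation is not in question.

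**What to change.** - **SAP 13.1, Table 10.1 and T_SD1:** use all allocated patient numbers as the base. Add rows by randomised arm and site for randomised; randomised and not dosed; withdrawn on baseline histology; and with and without paired Ki67, each with reasons.
- **Labels:** call the primary Ki67 set modified ITT, observed-case. Reconcile Protocol 6.7 and 13.1 with SAP 9 and 12.1. Tie in the efficacy analysis set that Protocol 13.4 uses and 13.1 does not define.
- **Sensitivity analysis:** in Protocol 13.4, or in the separate efficacy plan that SAP 3 implies, add one missing-data analysis of ΔKi67, for example placebo-based imputation, over randomised patients with a valid baseline index. Report separately those without one.

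All of this should be settled before the code is broken. The cost is a few table rows and one short program, with no new data. The drawback is that imputation will be imprecise at about 10 per arm, so it should be read as a check on the primary result and not as a replacement for it.
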